Effect of High Rebound Mattress Toppers on Sleep and Sleep-Related Symptoms

Study Protocol

NCT03055156

August 4, 2015

EFFECTS OF HIGH REBOUND MATTRESS TOPPERS ON SLEEP AND SLEEP-RELATED SYMPTOMS

The purpose of the study is to evaluate effects of high rebound mattress toppers (i.e., airweave®) on sleep and sleep-related symptoms and daytime performance. This proposal involves a clinical trial in patients visiting the Stanford Sleep Clinic.

Background:

airweave® is a high rebound mattress designed with a structure that allows breathability. In recent studies, we found that young and old healthy males using airweave® had more effective heat loss (i.e. a larger decline in core body temperature following sleep onset) and enhanced deep sleep during the initial phase of nocturnal sleep than when they used a low rebound pressure-absorbing mattress topper. The subjects who slept with airweave® also had improved subjective performance on the following day (1). This evaluation was done in a small number of subjects (10 and 20, respectively) in a Sleep Clinic (Ota Sleep Science, Kawasaki) in Japan and was reported at the SLEEP 2013 and 2014 meetings (1,2). Although [name] (The PI of the proposal) advised the research design, Stanford University was not officially involved in these studies. Based on these results, [name] and airweave® initiated a sponsored research project (SPO#110640) in 2013, and conducted field studies at IMG academy focusing on the effects of high rebound mattress toppers on sleep and athletic performance. Because the preliminary results are promising (3), we strongly believe that we need further studies to confirm the results.

In this new proposal, we propose to confirm and extend these initial findings using patients at the Stanford Sleep Disorders Clinic.

The goal of the study will be to see if patients with various sleep disorders slept better differently depending on mattresses (airweave® versus Tempur-Pedic® mattress topper).

Materials & Methods:

The study will be conducted over a 4-year period to compare the effects of airweave® with Tempur-Pedic® mattress toppers on top of regular mattress (equipped in the Stanford Sleep Disorders Clinic) on sleep and core body temperature. Currently, several different types of mattresses are equipped at the clinic, and we first plan to standardize the mattresses in all rooms at the clinic in order to avoid any confounding factor for the evaluation. Sleep will be evaluated using polysomnography (PSG) using metrics to evaluate sleep (e.g. sleep latency, wake after sleep onset (WASO), sleep efficiency, and delta wave EEG power) and sleep-related symptoms (e.g. apnea hypopnea index, periodic leg movements and position changes).

In healthy volunteers, the major effect of airweave® was a drop in core body temperature (monitored using a rectal probe) shortly after sleep onset (1,2). Additional weaker effects on sleep quality (i.e., increase in deep slow wave sleep and change in EEG delta power) that were expected based on the larger drop in temperature were also observed (1,2). At the sleep clinic, measuring rectal temperature using a rectal temperature probe would be difficult, since we plan to recruit from “patients that visit the clinic”. We therefore propose to monitor core body temperature using VitalSense, an ingestible capsule telemetry from Philips/Respironics (4). The telemetry compares in size to a large gel capsule and will be swallowed with liquid. The ingestible VitalSense temperature capsule easily travels and passes through the gastrointestinal tract without affecting other bodily functions and will wirelessly send temperature data continuously to the receiver placed in the recording room. Patient will have the option to use the capsule as a suppository if they prefer.

We will analyze sleep and sleep related symptoms in segments (e.g. hourly or every 2-hours) as

well as continuously over the entire night, since the major effects on the core body temperature are seen during the initial phase of sleep (1,2). Finally, we will collect subjective data on how well patients slept, which is standard clinic protocol after a sleep study.

To use a patient population will dramatically reduce cost and will allow us to study a large number of subjects. The pilot study was performed in healthy volunteers and as a cross-over design, whereas the proposed study will use a parallel randomized design in a larger sample. We expect that the majority of patients that participate in the study will have sleep apnea (or suspected sleep apnea), but at the end of the study, we will also have a considerable patient population that suffer from insomnia, restless legs syndrome and hypersomnia with various origins. A patient's symptoms and diagnosis will be recorded using the Alliance Sleep Questionnaire (5), a comprehensive, branching logic questionnaire that is used as standard of care at the clinic to evaluate severity and types of sleep problem. Doctor based diagnosis will be also extracted from EPIC (our Electronic Medical Record System). Based on this information, we will systemically analyze effects that are seen in specific diseases or patients with specific characteristics.

Year 1:

As mentioned above, preliminary data used a cross over design and a rectal probe in a small number of healthy subjects. This is an ideal design, but would be very costly to perform at the sleep clinic. Therefore it is difficult to extrapolate the necessary sample size to observe a significant effect using a parallel design and the VitalSense in a patient population. In the first year, we will include 80 patients (40/40 for airweave® and Tempur-Pedic® toppers) and use that data to calculate the sample size needed in order to see statistical effects. We will actively recruit patients with insomnia, since roughly 80% of patients who visit clinic are seen for sleep apnea, and since some insomnia patients may have temperature dysregulation which may partially contribute to their sleep symptoms. An interim analysis will be performed at the end of year 1, once we have studied 40 cases in both arms.

Depending on what is seen in the subgroup of patients with insomnia complaints (we expect the effect to be bigger, especially for those with difficulties with falling sleep, and more clinically meaningful), we will discuss whether it would make sense to focus the rest of the study on patients that have complaints of insomnia.

Years 2-4:

We will include 80/80 patients each year. Year 2 we expect to reach a total of ~ 240 patients, year 3 we will have ~400 and we should have ~ 560 patients in both arms at the end of year 4.

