Effect of High Rebound Mattress Toppers on Sleep and Sleep-Related Symptoms

Statistical Analysis Plan

NCT03055156

October 13, 2020

SPSS Statistics for Macintosh, version 26 (IBM corp, Armonk, NY) was used for all analysis.

To compare topper effects on sleep [TST, SE, SL, WASO, % of stages of Wake, REM, N1, N2, N3 out of TST], sleep related-factors [Position change frequencies, AHI, and heart rate], and VAS, independent sample t-tests were used.

Topper effects on Core body temperature (CBT) was analyzed using two-way mixed method ANOVA with time and topper type as effects. Topper effects on Mean EEG delta spectral power per second over 90 mins was analyzed using independent sample t tests for each 90 min time bin from lights off (i.e. 0-90min, 90-180 min, 180-270 min, 270-360min).

Significance levels for all analysis were set to $p=0.05$.

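### The core-temperature model has no route or baseline term, the patient chooses the route at an unstated time, and the SAP does not say which term tests the topper.

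*Protocol*

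**What the plan says.** Materials & Methods in the protocol describes an ingestible telemetry capsule. The default is that "The telemetry compares in size to a large gel capsule and will be swallowed with liquid", followed by "Patient will have the option to use the capsule as a suppository if they prefer". The signal is continuous: the capsule "will wirelessly send temperature data continuously to the receiver placed in the recording room".

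The design differs from that of the supporting data. Under Year 1, the "preliminary data used a cross over design and a rectal probe in a small number of healthy subjects"; here, "the proposed study will use a parallel randomized design in a larger sample".

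The temperature hypothesis appears in two forms. Background describes the earlier result as "a larger decline in core body temperature following sleep onset", which is a difference in change over time. Expected results says that the test topper should lower core temperature, which reads as a difference in level.

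The SAP gives the analysis in one sentence: "Topper effects on Core body temperature (CBT) was analyzed using two-way mixed method ANOVA with time and topper type as effects". It names no route term, baseline term or time-by-topper interaction, and does not say whether temperature enters as recorded or relative to an earlier value. Neither document says that the route is recorded, when the patient chooses it relative to allocation, or who knows the topper when the choice is made.

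**The concern.** Temperature is the outcome on which the rationale rests: Materials & Methods presents the fall in core temperature as the leading finding in healthy volunteers, and the sleep effects as following from it. The protocol also standardizes the mattresses in all rooms to keep out confounding, yet leaves the sensor site to preference and out of the model.

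In a parallel comparison, a patient's usual temperature level and any offset between gut and rectum sit inside the difference between arms when the topper is judged on average level. If the route is unrelated to the topper, this costs precision. If patients or staff know the topper before the route is chosen and route use then differs by arm, it also shifts the estimate, and a model with only time and topper cannot detect that.

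How much this matters depends on which term is the test, and the SAP does not say.

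**Working it through.** **The plan's own figures.** The documents give no SD, effect size or power for temperature. The only figures to reproduce are the recruitment totals: 80, then 80 + 160 = 240, 240 + 160 = 400 and 400 + 160 = 560. They agree. The arms are therefore 40 each at the end of year 1 and about 560 / 2 = 280 each at the end of year 4.

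**Which term carries what.** Write a patient's temperature at time t as the arm's mean curve + personal level b + site offset s(t) + error.
- The topper main effect compares patients' averages over time. It carries b and the average of s.
- The time-by-topper interaction compares the shape of the curves after each patient's own mean is removed. There b cancels, and so does s if it is constant. A site difference that changes over time does not cancel.

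**Variance added to the main effect by mixed sites.** Assumptions: person SD 0.25 °C (variance 0.0625), share p using the suppository, site offset d. Added variance = p(1 − p)d² / 0.0625.
- p = 0.1, d = 0.1: 0.0009 / 0.0625 = 1.4%
- p = 0.2, d = 0.2: 0.0064 / 0.0625 = 10.2%
- p = 0.3, d = 0.3: 0.0189 / 0.0625 = 30.2%

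**Bias in the main effect if route use differs by arm.** Bias = difference in share × offset. A 10-point difference with a 0.2 °C offset gives 0.10 × 0.2 = 0.02 °C.

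**Gain from a baseline, main effect only.** With correlation r between the pre-lights-off mean and the later level, the standard error relative to no baseline is √(1 − r²) for a covariate and √(2(1 − r)) for a change score.

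| r | Covariate | Change score |
|---|---|---|
| 0.5 | 0.87 | 1.00 |
| 0.7 | 0.71 | 0.77 |
| 0.8 | 0.60 | 0.63 |

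The covariate does better at each r shown, and the change score gains nothing at r = 0.5. In patient numbers, the covariate is worth 1/(1 − r²) = 1.3, 2.0 or 2.8 times the sample, for this term alone.

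**Simulation of the mixed ANOVA.** Assumptions: 7 time points, independent errors with SD 0.1 °C, person SD 0.3 °C unless stated, two-sided 0.05. Entries are rejection rates.

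| Scenario | Main effect | Interaction |
|---|---|---|
| No topper effect; 0.2 °C constant offset, 30% suppository in both arms, 40 per arm | 0.048 | 0.046 |
| Same offset; 20% v 40% suppository, 40 per arm | 0.090 | 0.056 |
| Same offset; 20% v 40% suppository, 280 per arm | 0.32 | 0.045 |
| Extra fall of 0.1 °C by the end of the window, one site, 40 per arm | 0.11 | 0.86 |
| Same fall, person SD set to 0 | 1.00 | 0.84 |

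Personal level and a constant site offset affect the main effect and leave the interaction alone.

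**A site difference that changes over time.** Suppose, as a pure assumption, that swallowed capsules read 0.2 °C low at the start and the error then decays (person SD 0.25 °C, no topper effect). With 20% v 40% suppository use, the interaction rejects in about 0.15 of trials at 40 per arm and 0.82 at 280 per arm. With equal use it rejects in about 0.05.

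**The case against.** The strongest reply is that the hypothesis is a larger fall, that a mixed ANOVA tests this through the interaction, and that constant offsets cancel there. This is correct, and the simulation bears it out. It limits the precision figures and the constant-offset bias to the main effect. It does not dispose of the point, because the SAP never names the interaction, Expected results is worded as a level, and the cancellation fails if the site difference changes over time and route use differs by arm.

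A second reply is that randomization protects the comparison. It does when route is unrelated to arm: error rates were nominal in that case. A reader might infer that the comparison is already biased by route. The documents do not support that. They are silent on when the choice is made, so the bias is possible but not shown, and a 10-point difference in route use moves the level by only 0.02 °C under the assumed offset.

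Third, the move from crossover to parallel groups might be read as a flaw in itself. The Year 1 section calls the crossover ideal but very costly, admits that sample size is hard to extrapolate from it, and uses the first 80 patients to set the number needed. That is an open trade-off.

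Two further inferences fail. One is that a swallowed capsule is disturbed by liquid or gut position just when the effect is expected: the protocol does not say when the capsule is swallowed and gives no data on such a disturbance. The other is that the SAP analyses temperature as recorded: it does not say either way.

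Finally, a pre-lights-off baseline could itself carry a route-specific disturbance. That is fair, and is why route and time of use should be recorded and route kept in the model beside the baseline.

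**Conclusion.** The point holds in a limited form. The route is chosen by the patient, at an unstated time, with no provision for recording it. The temperature model names neither route nor baseline, and no term is named as the test of the topper.

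For the topper main effect, mixed sites cost 1–30% in variance under the assumed ranges, and a baseline covariate would cut the standard error to 87%, 71% or 60% at correlations of 0.5, 0.7 or 0.8. Bias arises only if route use differs by arm. It would be tempting to apply the 1.3 to 2.8-fold gain in patients to temperature as a whole. It applies only to the level contrast with a covariate, and not to the larger fall after sleep onset.

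For the interaction, constant differences do no harm; only site differences that vary over time and go with unequal route use would. Every SD, offset, share and correlation here is an assumption, and the simulated interaction rates also assume independent errors. Naming the test and fixing the order of choice do not depend on those values.

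**What to change.** In the protocol, Materials & Methods: have the patient choose swallowed or suppository use before the topper is assigned, and record the route and the time of use. The patient's option stays as it is.

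In the SAP, temperature sentence:
- Name the time-by-topper interaction as the test of a larger fall.
- For the level contrast, add the patient's own mean temperature before lights off as a covariate (not a change score), and add route. Define the baseline window in advance.
- Report the topper effect among patients who swallowed the capsule as a sensitivity analysis.

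The cost is two recorded fields, one ordering rule, two model terms and one sentence naming the test. The baseline needs no new measurement if the capsule is already transmitting before lights off. The downside is that patients without a stable pre-lights-off reading need an imputed baseline or leave that model. The SAP is written in the past tense. If recording is already complete, the ordering rule can no longer be applied; route should then be recovered from source records where possible, and its balance between arms reported.

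### The plan specifies no stratification by diagnosis and the topper comparisons carry no diagnosis term, although insomnia and apnea patients are deliberately mixed (low priority)

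*Protocol*

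**What the plan says.** **Allocation.** Materials & Methods in the protocol says that "the proposed study will use a parallel randomized design in a larger sample". Year 1 adds the numbers: "In the first year, we will include 80 patients (40/40 for airweave® and Tempur-Pedic® toppers". Years 2-4 continue at 80 per arm each year. Neither document mentions a stratification factor, blocks or minimisation.

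**Case mix.** Materials & Methods expects apnea, confirmed or suspected, in most participants. Year 1 then plans enrichment: "We will actively recruit patients with insomnia, since roughly 80% of patients who visit clinic are seen for sleep apnea". No target number of insomnia patients is given.

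**Use of the insomnia result.** Year 1 ties a discussion about the focus of the remaining study to this subgroup: "Depending on what is seen in the subgroup of patients with insomnia complaints (we expect the effect to be bigger". The year 1 data are also to supply the sample size calculation.

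**Diagnosis data.** Materials & Methods records symptoms and diagnosis through a standard-of-care questionnaire and the medical record, and intends to look at effects by disease.

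**Analysis.** The SAP uses two-sample t-tests for the sleep measures, related factors, VAS and binned delta power. For core body temperature it uses a mixed ANOVA with time and topper. No diagnosis term appears in any of these.

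**The concern.** The protocol itself treats diagnosis as something that changes the topper effect, and insomnia patients plausibly also differ from apnea patients in baseline sleep latency and wake. A factor of that kind is normally balanced at allocation, entered in the model, or both. Here neither is written down.

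Two things could suffer. First, between-diagnosis variance stays in the error term of every overall comparison, and in any SD taken from year 1 to size the rest of the trial. Second, the split of insomnia patients between toppers may be left to chance in the subgroup that feeds the discussion about years 2-4.

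**Working it through.** **Plan's own figures.** 40 + 40 = 80 in year 1. Adding 160 a year gives 240, 400 and 560, as the protocol states. Years 2-4 therefore hold 560 − 80 = 480 patients. No effect size, SD, power or insomnia number is given, so everything below rests on assumed inputs. Tests are taken as two-sided at 0.05; the SAP gives the level but not the sidedness.

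**1. Variance due to diagnosis.** Let p be the insomnia share and d the insomnia-apnea difference in within-group SDs. The share of total variance is p(1−p)d² / [1 + p(1−p)d²].

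| p | d | p(1−p)d² | Share |
|---|---|---|---|
| 0.2 | 0.5 | 0.04 | 0.04/1.04 = 4% |
| 0.5 | 0.5 | 0.0625 | 0.0625/1.0625 = 6% |
| 0.2 | 1.0 | 0.16 | 0.16/1.16 = 14% |
| 0.5 | 1.0 | 0.25 | 0.25/1.25 = 20% |

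Required sample size is proportional to variance. An SD that ignores diagnosis therefore inflates the year 1 calculation by a factor of 1.04 to 1.25. Interval widths in the overall comparison fall by 1 − √0.96 = 2% to 1 − √0.80 = 11% once the term is in the model.

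**2. How uneven could the insomnia split be?** The clinic mix without enrichment gives 20% × 80 = 16 non-apnea patients, used here as an illustrative insomnia number m. With 40/40 fixed and no stratification, the split is hypergeometric.

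- m = 16: 6/10 or worse 40%; 5/11 or worse 16%; 4/12 or worse 5%.
- A split of 2:1 or worse: 16% at m = 16, 9% at m = 24, 1% at m = 32.

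**3. What does an uneven split cost?** The 95% half-width in SD units is t(0.975, m−2) × √(1/n₁ + 1/n₂).

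| Split | Half-width | Against an even split |
|---|---|---|
| 8/8 | 2.145 × 0.500 = 1.07 | – |
| 6/10 | 2.145 × 0.516 = 1.11 | +3% |
| 5/11 | 2.145 × 0.539 = 1.16 | +8% |
| 16/16 | 2.042 × 0.354 = 0.72 | – |
| 12/20 | 2.042 × 0.365 = 0.75 | +3% |

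Averaged over chance splits at m = 16, efficiency relative to 8/8 (4n₁n₂/m²) is 0.95. Subgroup power from the noncentral t at effects of 0.5, 0.8 and 1.0 SD is 15%, 32% and 46% with 8/8, against 15%, 31% and 44% on average without stratification. For 80% power the subgroup would need about 63, 25 or 16 per arm (normal approximation), against 8.

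**4. Effect on the overall year 1 contrast.** A 6/10 split makes the insomnia shares differ by 4/40 = 10 points. With d of 0.5 to 1.0 this moves the unadjusted topper difference by 0.05 to 0.10 SD. For 5/11 the gap is 6/40 = 15 points and the shift 0.075 to 0.15 SD. The standard error of a 40/40 contrast is √(2/40) = 0.22 SD.

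**The case against.** - **Is randomisation unstratified?** A reader might infer so. The documents do not say it; they are silent on the method. Only the absence of a specification can be claimed.
- **Does an uneven split bias the insomnia result?** That is also tempting, but it does not follow. Under randomisation the within-insomnia comparison is unbiased at any split. The shift in the overall contrast is ordinary randomisation error, already covered by its standard error, and it shrinks as enrolment approaches 560.
- **Are there at most 16 insomnia patients?** The documents do not bound the subgroup there. The 80% figure describes clinic visitors, while the protocol plans to enrich. It also defines the subgroup by insomnia complaints, which apnea patients may share. At 32 a badly uneven split is unlikely.
- **Does the insomnia result determine later recruitment?** The protocol promises only a discussion; no rule is triggered.
- **Does the gain need stratified allocation?** No. The 4% to 20% comes from the model term, and the fall from 1.07 to 0.72 SD comes from having more insomnia patients. Neither depends on how toppers are allocated.

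All five stand. They remove most of the weight from chance imbalance. They leave untouched the mismatch between a trial built on mixed diagnoses and an analysis that ignores diagnosis.

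**Conclusion.** The point holds as a low-priority improvement. The stated tests ignore a recorded factor that the protocol expects to matter. Adjusting for it would remove about 4% to 20% of outcome variance, provided that insomnia and apnea differ by 0.5 to 1.0 SD and insomnia forms 20% to 50% of the sample. Both ranges are assumptions, and with a smaller difference the gain approaches zero.

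Stratified allocation is a minor addition, worth about 0.5 to 2 points of subgroup power on average at 16 insomnia patients. The year 1 insomnia result would be imprecise even with a perfect split; the number of insomnia patients matters far more than their balance.

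**What to change.** 1. **Analysis.** Add insomnia complaint (yes/no, from the questionnaire already collected) as a factor in each topper comparison. The t-tests become linear models with topper and complaint, and the temperature ANOVA gains complaint as a between-patient factor. Class patients with both complaints as yes. Use the adjusted residual SD when sizing the later years. The cost is close to nil.
2. **Allocation.** State the randomisation method, and use permuted blocks within the same two strata. This needs a second list and one screening field, with the total unchanged. The complaint must be recorded before a topper is assigned, so the timing of the questionnaire has to be confirmed. If allocation is already complete, only the analysis change applies.
3. **Optional.** Set a year 1 target number of insomnia patients within the 80. Having 32 instead of 16 would cut the subgroup half-width from about 1.07 to 0.72 SD, but may slow enrolment. This is a trade-off for the sponsor to weigh, and the first two changes do not depend on it.
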